7.4.5 Physical Examination

Physical examination will be conducted at Screening, Admission and at the day of Discharge or at early termination.

A full physical examination will include review of general appearance, hair and skin, head, eyes, ears, nose and throat, neck, chest, abdomen, dentition, cardiovascular, musculoskeletal and neurological systems. The physical examination is to be conducted by the Investigator or designated fully trained representative.

7.4.6 Body Height and Weight

Body height and weight will be recorded at the Screening Visit and BMI will be calculated using the following formula:

$$\text{BMI} = \frac{\text{weight in kilograms}}{\text{height in meters}^2} = \frac{kg}{m^2}$$

The BMI will be used to assess eligibility for enrollment.

7.4.7 Vital Signs

Vital signs (systolic and diastolic blood pressure, respiratory rate and pulse rate) will be measured at Screening Visit, Admission and on every day of confinement (Day 1 to Day 5). On Day 1 to Day 4, vital signs will be assessed within 60 minutes prior to product use and 60 minutes \pm 10 minutes after each product use period (fixed puffing regimen and *ad libitum* use).

All parameters will be recorded in supine position after the subject has rested for at least 5 minutes. At Screening and Admission, the subject should have abstained from smoking for at least 15 minutes prior to measurement.

Confidentiality Statement

Data and information contained in this document are considered to constitute trade secrets and confidential commercial information, and the legal protections provided to such trade secrets and confidential information are hereby claimed under the provisions of applicable law. No part of this document may be publicly disclosed without the written consent of Philip Morris Products S.A.

7.4.8 Other Clinical Assessments

7.4.8.1 Electrocardiogram

A standard 12-lead ECG will be recorded after the subject has rested for at least 10 minutes in supine position at Screening, Admission and on every day of confinement (Day 1 to Day 5). During the investigational product-use days (Day 1 to Day 4) ECG will be recorded after the fixed puffing regimen and after the *ad libitum* use. All ECGs will be reviewed on an ongoing basis by the Investigator or designee. The following parameters will be documented: heart rate, PR interval, QRS interval, QT interval, and QTc interval corrected according to Bazett's formula and Fridericia's formula. Every ECG has to be assessed as normal, abnormal – clinically not significant, or abnormal – clinically significant. A diagnosis has to be provided in the CRF for all ECGs assessed as abnormal – clinically significant. Any print-outs of ECGs on thermo-sensitive paper must be photocopied and stapled together for inclusion in the source documents.

7.4.8.2 Spirometry

Spirometry without bronchodilator will be performed at Screening Visit and Discharge in accordance with the 2005 guideline of the American Thoracic Society (ATS)/European Respiratory Society (ERS) Joint Task Force on the standardization of spirometry (16). Spirometry predicted values will be standardized to the National Health and Nutrition Examination Survey III predicted set (17).

Assessed parameters will include: FEV₁, FEV₁ % predicted, FVC, FVC % predicted, FEV₁/FVC.

All personnel performing spirometry testing should have the appropriate training and quality control measures should be put into place and be properly documented. The testing will be performed in sitting position at rest for at least 15 minutes and at least 1 hour after having stopped using cigarettes (Screening Visit).

7.5 Biomarker Assessment

7.5.1 Biomarkers of Exposure to Nicotine

For PK analysis of plasma nicotine levels, venous blood samples will be obtained according to the investigational site standard operating procedures (SOPs) at the following timepoints:

a) Fixed puffing (Morning: Days 1 through 4):

A total of 10 blood samples will be taken for fixed puffing PK parameter estimation. One blood sample will be taken prior to the product use (T_0 fix) 15 minutes \pm 5 minutes (T-1). Thereafter in relation to T_0 fix, blood will be drawn at the following time points: T1 after 2 minutes \pm 1 minute, T2 after 4 minutes \pm 1 minute, T3 after 7 minutes \pm 1 minute, T4 after 10 minutes \pm 1

Confidentiality Statement

Data and information contained in this document are considered to constitute trade secrets and confidential commercial information, and the legal protections provided to such trade secrets and confidential information are hereby claimed under the provisions of applicable law. No part of this document may be publicly disclosed without the written consent of Philip Morris Products S.A.

minute, T5 after 15 minutes \pm 2 minutes, T6 after 30 minutes \pm 2 minutes, T7 after 1 hour \pm 5 minutes, T8 after 2 hours \pm 5 minutes, and T9 after 4 hours \pm 5 minutes.

b) *Ad libitum* use (Afternoon: Days 1 through 4):

A total of 8 blood samples will be taken for the *ad libitum* PK parameter estimation. One blood sample will be taken prior to product use ($T_{0 \text{ ad lib}}$) at 15 minutes \pm 5 minutes (T-1). In relation to $T_{0 \text{ ad lib}}$, blood will be drawn at the following time points: T1 after 10 minutes \pm 1 minute, T2 after 20 minutes \pm 2 minutes, T3 after 30 minutes \pm 2 minutes, T4 after 40 minutes \pm 5 minutes and T5 after 1 hour \pm 5 minutes, T6 after 2 hours \pm 5 minutes, and T7 after 4 hours \pm 5 minutes.

c) Day of Discharge (Day 5)

A total of 5 blood samples will be taken on Day 5. Blood samples will be taken in relation to $T_{0 \text{ ad lib}}$ from Day 4 at the following time points: T1 after 14 hours \pm 30 minutes, T2 after 16 hours \pm 30 minutes, T3 after 18 hours \pm 30 minutes, T4 after 20 hours \pm 30 minutes and T5 after 24 hours \pm 30 minutes.

The actual collection time of each blood sample must be recorded on the CRF.

Since the test for nicotine concentration is highly sensitive, precautions should be taken during blood sampling and processing to prevent the contamination of samples with environmental nicotine.

7.5.2 CYP2A6 Activity

CYP2A6 activity will be assessed on Day 1 prior to P3P use. CYP2A6 activity drives the metabolism of nicotine to cotinine and subsequent metabolites. In this study the CYP2A6 activity will be measured in plasma using the metabolic molar ratio of *trans*-3'-hydroxycotinine/cotinine.

7.6 Laboratory Assessments

7.6.1 Clinical Chemistry, Hematology, and Urine Analysis Safety Panel

A blood sample for hematology and clinical chemistry analysis will be taken from each subject at Screening, Admission and Day 2 to Day 5. Subjects should be fasting for at least 6 hours prior to sampling, except at Screening where non-fasting samples can be used. Tests will be conducted at a local laboratory (Appendix B). A urine sample will also be collected from each subject for urine analysis. Parameters to be tested are listed in Table 4.

Confidentiality Statement

Data and information contained in this document are considered to constitute trade secrets and confidential commercial information, and the legal protections provided to such trade secrets and confidential information are hereby claimed under the provisions of applicable law. No part of this document may be publicly disclosed without the written consent of Philip Morris Products S.A.

Table 4 Clinical Laboratory Parameters for Safety Panel

Hematology	Clinical Chemistry	Urine Analysis

 • Hematocrit • Hemoglobin • Mean corpuscular hemoglobin • Mean corpuscular hemoglobin concentration • Mean corpuscular volume • Platelet count • Red blood cell count • White blood cell (WBC) count • Differential WBC count: 
 • Neutrophils • Basophils • Eosinophils • Lymphocytes • Monocytes 	
 • Albumin • Total protein • Alkaline phosphatase • Alanine aminotransferase • Aspartate aminotransferase • Blood urea nitrogen • Creatinine • Gamma-glutamyl transferase • Fasting glucose* • Lactate dehydrogenase • Potassium • Sodium • Total bilirubin • Direct bilirubin • Total cholesterol • Triglycerides 	
 • pH • Bilirubin • Glucose • Nitrite • Red blood cell traces • Protein • Specific gravity

* Except at Screening where non-fasting glucose will be assessed

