6.6.2 Dietary and Activity Restrictions

A standard diet will be designed for the whole confinement period. For each meal, the caloric and fat content should be controlled in order to avoid a “high-fat” diet. The FDA guidance on food-effect studies for bioequivalence testing identifies a “high-fat” diet as a diet which contains “approximately 50 percent of total caloric content of the meal [from fat] and is high in calories (approximately 800 to 1000 calories) (13).”

Subjects are not allowed to bring their own food or beverages to the investigational site. Meals will be served according to the schedules provided in section 9. Additional light snacks, fruits, and raw vegetables can be distributed to the subjects without restrictions at any time during confinement (except during the product use periods) as long as they comply with the standard diet. Consumption of water is allowed as desired. Consumption of quinine-containing drinks (e.g., tonic water) is not allowed. Subjects should refrain from ingesting foods or beverages containing grapefruit or seville-type (sour) oranges and marmalade from 7 days prior to Day - 1 and throughout the study. The same menu and meal schedule will be administered uniformly for all subjects. Fasting state has to be observed for at least 6 hours prior to blood drawings for the safety laboratory at Admission, and on Days 2, 3, 4 and 5.

Subjects should refrain from strenuous and/or unaccustomed exercise throughout the entire course of the study.

Confidentiality Statement

Data and information contained in this document are considered to constitute trade secrets and confidential commercial information, and the legal protections provided to such trade secrets and confidential information are hereby claimed under the provisions of applicable law. No part of this document may be publicly disclosed without the written consent of Philip Morris Products S.A.

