8.4 Reporting of Other Events Critical to Safety Evaluations

8.4.1 Abnormal Results of Laboratory Tests

Any clinical safety laboratory test result that is outside of the normal reference range will be reviewed by the Investigator and assessed for clinical significance according to its severity. The severity of abnormal laboratory test result must be assessed using CTCAE version 4.03 grading scales (Appendix C). Any clinical safety laboratory test result that is outside of the normal reference range will be reviewed by the Investigator and assessed for clinical significance according to its severity. Whenever that grading scheme is not available for the laboratory result of concern, the Investigator should assess the severity and the clinical significance of that result using his/her medical judgment.

Subjects with clinically significant abnormal laboratory values at Screening will not be enrolled. Abnormal laboratory test results detected at the Screening Visit whose CTCAE grades are 2 or higher or still are CTCAE grade 1 and deemed clinically significant are usually concomitant disease or a manifestation of one and must be recorded accordingly. However, in some instances, they may be assessed as AEs (and therefore must be handled according to the directions in section 8.2) or as manifestations of already reported AEs. This decision will require a careful assessment of the abnormal result within the clinical context on a case-by-case basis and will depend on the Investigator's medical judgment.

Abnormal laboratory test results detected after the Screening Visit whose CTCAE grades are 2 or higher or still are CTCAE grade 1 and deemed clinically significant must be either recorded as AEs (and handled according to the directions in section 8.2) or linked to a concomitant disease or still to an already reported AE.

The principles for assessing and reporting abnormal laboratory test results, emerging after the Screening Visit, using CTCAE 4.03 grading scales are set up in Table 6:

Table 6 Principles for assessing and reporting abnormal laboratory test results

Grading	Clinically significant?	Is it a grade increase from previous results in study?§	Report?
Grade 1	No	Not applicable	No
Grade 1	Yes	No	No*
Grade 1	Yes	Yes	Yes, as AE or linked to an already reported AE
Grade 2 or higher	No/Yes	No	No*
Grade 2 or higher	No/Yes	Yes	Yes, as AE or linked to an already reported AE

Confidentiality Statement

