Data and information contained in this document are considered to constitute trade secrets and confidential commercial information, and the legal protections provided to such trade secrets and confidential information are hereby claimed under the provisions of applicable law. No part of this document may be publicly disclosed without the written consent of Philip Morris Products S.A.

* in this situation, this abnormal lab test result is either a manifestation of a concomitant disease or of an already reported AE.

§ grade increase in this context means the value is higher than the one from the Screening Visit.

In general, laboratory values will be recorded as “increased <lab parameter>” or “decreased <lab parameter>” to ensure consistency of recording/coding.

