## 4.1 Definitions for Statistical Analysis

The following special terms are used in this SAP:

Baseline	For PK/PD analysis and VAS-craving assessment, baseline is defined as the last assessment prior to time point of start of product use at the fixed puffing regimen ( $T_0 \text{ fix}$ ) for fixed puffing regimen and as the last assessment prior to time point of start of first product use at the ad libitum use period ( $T_0 \text{ ad lib}$ ) for ad libitum use, for each study day of exposure. For all the other endpoints, the baseline is defined as the last available assessment prior to $T_0 \text{ fix}$ on Day 1, except for vital signs, where baseline is defined as the last assessment prior to $T_0 \text{ fix}$ for each study day of exposure.
Safety follow-up	After discharge on Day 5 or after discontinuation, a 7-day safety follow-up will be done
End of Study	The end of the study (EOS) for a subject is defined as either the Discharge at Day 5, or the date of early termination of the subject, plus the 7 days for the Safety Follow-up Period. The end of the whole study corresponds to the individual EOS of the last subject.
Enrollment	On Admission Visit for eligible subjects after all applicable inclusion and exclusion criteria have been satisfactorily assessed and met.
Randomization	Assignment to the respective sequence of product use at Day 2.
Screen failure	Subject who signs the ICF but is not enrolled.

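### Table 6 judges fasting post-use laboratory results against a Screening value that may be non-fasting, so some new glucose or triglyceride abnormalities can miss the AE label

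*Protocol*

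**What the plan says.** **Fasting.** Protocol 7.6.1 states: "Subjects should be fasting for at least 6 hours prior to sampling, except at Screening where non-fasting samples can be used". For glucose, the Table 4 footnote goes further: "Except at Screening where non-fasting glucose will be assessed". Section 6.6.2 requires at least 6 hours of fasting "prior to blood drawings for the safety laboratory at Admission, and on Days 2, 3, 4 and 5". Screening can fall up to 3 weeks before Admission.

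**AE rule.** Table 6 in Protocol 8.4.1 reports a clinically significant Grade 1 result, or any result of Grade 2 or higher, only when a third condition is met. The column header reads "Is it a grade increase from previous results in study". The footnote to that header says "grade increase in this context means the value is higher than the one from the Screening Visit". When the condition fails, the entry is `No*`, and the second footnote explains: "in this situation, this abnormal lab test result is either a manifestation of a concomitant disease or of an already reported AE".

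**Enrollment limit.** The same section says "Subjects with clinically significant abnormal laboratory values at Screening will not be enrolled". An abnormal Screening value that is not clinically significant does not bar entry.

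**Grading.** Appendix C, Table C1 gives hyperglycemia cut-offs on a fasting scale only. The SAP (12.6.5.4) derives the grades by program.

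**SAP baseline.** SAP 4.1 states: "For all the other endpoints, the baseline is defined as the last available assessment prior to" the start of fixed puffing on Day 1. For laboratory data the scheduled sample that fits is Admission (Day -1), and SAP 12.6.5.4 builds changes and shift tables on it.

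**The concern.** Glucose and triglycerides depend on meals. If the comparator follows a meal and the result under test is fasting, the comparator can already be raised for a reason unrelated to the subject's fasting state. The rule then finds no increase, although the subject's own fasting value has risen since Admission. The mismatch is sharper for glucose, because a non-fasting Screening value is graded on fasting cut-offs.

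Protocol 12.6.3 makes AE data the primary safety assessment and assigns each laboratory AE to the product used the day before. A result that misses the AE label is therefore missing from the by-variant AE tables. The protocol (2.1.2) reports no human data on nicotine absorption from P3P, and 18 subjects are to be randomized, so single laboratory AEs carry some weight. The study would also run on two references: Screening for the AE rule and Admission for the shift tables.

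**Working it through.** The plan gives no figure to reproduce here. The check applies the documents' own grade boundaries and reporting rule to illustrative subjects.

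**Inputs from the documents.** From Table C1, in mg/dL:
- Glucose: Grade 1 is above the ULN to 160; Grade 2 is above 160 to 250.
- Triglycerides: Grade 1 is 150 to 300; Grade 2 is above 300 to 500.

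From Table 6: report if (Grade 1 and clinically significant, or Grade 2 or higher) and there is an increase over the comparator; otherwise `No*`.

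**Assumptions.** The subject values are hypothetical. The glucose ULN is taken as 100 and then 110 mg/dL, because the documents do not state it; the results are the same. Post-use results are taken as clinically significant. The Screening value is taken as not clinically significant, since otherwise the subject could not enroll. Each case was run with an increase read as a higher grade and as a higher value; both readings agree in every row.

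| Analyte | Screening (may be non-fasting) | Admission (fasting) | After P3P (fasting) | Rise from Admission | Against Screening | Against Admission |
|---|---|---|---|---|---|---|
| Glucose | 170, G2 | 90, G0 | 165, G2 | 165 − 90 = 75 | `No*` | Yes |
| Glucose | 150, G1 | 90, G0 | 150, G1 | 150 − 90 = 60 | `No*` | Yes |
| Triglycerides | 320, G2 | 140, G0 | 310, G2 | 310 − 140 = 170 | `No*` | Yes |
| Triglycerides | 250, G1 | 120, G0 | 240, G1 | 240 − 120 = 120 | `No*` | Yes |
| Glucose | 130, G1 | 90, G0 | 165, G2 | 165 − 90 = 75 | Yes | Yes |
| Triglycerides | 250, G1 | 120, G0 | 310, G2 | 310 − 120 = 190 | Yes | Yes |
| Triglycerides | 140, G0 | 120, G0 | 310, G2 | 310 − 120 = 190 | Yes | Yes |

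The first four rows change when the comparator changes; the last three do not. Masking therefore needs two things together: a Screening value already at Grade 1 or higher but not clinically significant, and a post-use result no higher than it in grade (or in value, on the footnote's literal wording).

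**The wording conflicts.**
- The Table 6 header refers to earlier study results in general, which would include Admission. Its footnote names Screening only.
- The header speaks of grade and the footnote of value. Triglycerides of 240 at Screening and 250 after use are an increase in value (250 > 240) but not in grade (both lie in 150 to 300).
- The prose of 8.4.1, repeated in SAP 12.6.5.4, says that a later result of Grade 2 or higher, or a clinically significant Grade 1, must be recorded as an AE or linked to a concomitant disease or an existing AE. It makes no comparison with Screening.

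The prose bears differently on the two kinds of masked case. A Grade 2 Screening result is, by the same section, usually recorded as concomitant disease, so the later result can be linked to it and both rules lead to no new AE. A Grade 1 Screening result that was not clinically significant need not have been recorded as anything. The prose then points to an AE, while Table 6 says `No*`.

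**The case against.** The strongest reply is that the prose rule governs and Table 6 only sets out principles. On that reading a post-use result with nothing to link to is recorded as an AE whatever Screening showed. This stands in part: for Grade 1 Screening values the defect is a conflict between two instructions, not a settled omission. It does not cover Grade 2 Screening values, where a recorded concomitant disease supplies the link.

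Second, the enrollment limit narrows the affected group, and in the Grade 1 case a later value that is no higher must be judged clinically significant when the Screening one was not. That stands, and it makes the situation less common. It does not exclude it.

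Third, AEs are collected from consent, and Protocol 8.1.3 judges pre-existing conditions from the same point, so a Screening reference has a logic of its own, and two references for two purposes are not in themselves an error. That also stands. The fault is the difference in fasting state, not the mere difference from the SAP baseline.

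A reader might also infer that post-use rises would disappear from the report. The documents do not support that. SAP 12.6.5.4 lists every value with its change from baseline, grade and clinical significance, tabulates abnormal results, and provides shift tables from the Admission value, most of them flagged for safety reporting.

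Nor do they support reading every Screening analyte as non-fasting: only glucose is non-fasting by rule, and for triglycerides it is permitted.

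**Conclusion.** The point holds in a limited form. As written, the Table 6 footnote can send a new fasting abnormality in glucose or triglycerides to `No*` when Screening was abnormal but not clinically significant and the fasting Admission value was normal. The consequence is confined to the AE label and the AE tables built from it; the laboratory listings and shift tables would still show the worsening.

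It is tempting to state the share of subjects affected by assuming a post-meal shift and a standard deviation. The documents give neither. Such a figure would also be conditional on the subject having the rise, and would have to allow for the grade and clinical-significance conditions. No frequency should be quoted.

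The conclusion rests on the quoted text and the Table C1 boundaries. The mg/dL values in the worked cases are illustrations only. It also takes the Admission blood sample to precede the product test. The row order of Table 8 suggests this, but no text says so, whereas Protocol 7.8.5 does say so for the cough assessment.

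**What to change.** 1. In the Table 6 footnote, for samples taken after P3P exposure (Days 2 to 5 and early termination), make the comparator the fasting Admission (Day -1) value, with Screening used only if the Admission result is missing.
2. Keep Screening as the comparator for the Admission sample itself, which otherwise would have no reference.
3. State in 7.6.1 and Table 8 that the Admission blood sample is taken before the product test. State the fasting condition in Table 12 as well: the early-termination entry gives none, although 7.6.1 and Appendix A note f except only Screening.
4. Bring the footnote, the column header (which earlier results count; grade or value) and the prose rule in 8.4.1 and SAP 12.6.5.4 into one consistent instruction.

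No extra samples or visits are needed, and AE reporting would share its reference with the SAP shift tables. The cost is a short text amendment and possibly a few more laboratory values reported as AEs.
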